In order to explore its efficacy, 100 participants will be randomized to receive either the app or an attention-matched control (AC). We will use self-report measures of alcohol use collected at 1-, 3-, and 6-months and changes in a biomarker of alcohol use collected at baseline, 3-, and 6-months to explore whether GP4PrEP reduces binge drinking compared with AC. We will also use data from a biomarker of PrEP adherence to explore whether GP4PrEP improves PrEP adherence vs. AC. Finally, we will also test whether GP4PrEP participants showed lower rates of STI incidence across the study period compared to AC. A baseline assessment battery will be used to collect data on alcohol and other drug use and factors that can affect medication adherence such as attitudes towards PrEP, barriers and facilitators to taking PrEP, stigma, and beliefs. Follow-up assessments will also assess a number of covariates that may be relevant to PrEP adherence over time, including side effects, health insurance coverage, financial strain, health-related quality of life, and social support. STI incidence at each quarterly routine PrEP care visit will also be collected by extracting this data from participants' electronic medical records. At these visits, participants are tested for Chlamydia and Gonorrhea at genital, rectal, and oral sites, syphilis, and HIV. At-home kits to collect dried blood spot (DBS) samples will be sent to participants at baseline (immediately after they enroll), at 3-months, and 6-months post-enrollment, using procedures used by several national laboratories and in several past studies. DBS samples will be analyzed for TFV-DP levels, a biomarker for adherence to PrEP, as well as phosphatidylethanol (PEth), a biomarker of alcohol consumption. At the Miriam PrEP clinic, limited research staff who are co-located in the clinic will inquire about PrEP patients' potential interest in

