4. Participant Population. *In order to approve research, the IRB must determine that the selection of participants is equitable and reasonably related to the purpose and aims of the research. The IRB must also consider whether adequate safeguards are in place to minimize any risks that are unique to vulnerable populations. To make this determination, the IRB must review all methods and materials used to contact and recruit potential participants, including letters, flyers, emails, etc.*

Criteria for inclusion in this study are: (1) Current male gender, (2) 18+ years old, (3) able to speak and read in English fluently, (4) heavy alcohol use in the past month (>5 drinks on a single occasion or >14 drinks in a week), (5) currently prescribed and actively taking PrEP, and (6) report missing > 3 PrEP doses in a row at least once in the past 3 months. Those who have (1) injected drugs in the past year, (2) screen positive for drug-related disorders, (3) report a history or risk of complicated alcohol withdrawal, or (4) are currently receiving counseling or medications for alcohol or drug addiction will be excluded. Participants must be fluent in English to participate. The target number of participants to be included in the study is 100, 50 in each condition.

5. Recruitment Methods

Participants will be recruited a variety of ways, including social media advertisements, flyers and business cards, and from an existing database, in which potential participants previously expressed interest in participating in various research studies with Smash Labs. Examples of images and text used in online advertisements are attached, as well as advertising palm cards. Initial contact will involve participants completing an online screener to determine their eligibility for the study. If determined eligible, participants will consent online, and give contact info. Research staff will call to verify participants' enrollment, further explain the consent and what's expected of them in the study, and answer any questions the participant may have. Research staff will be trained by PI and project coordinator. Screening data will be destroyed after study completion.

6. Compensation / Reimbursement

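### STI incidence is taken only from medical records, but recruitment is open and the protocol states no route to those records, so the comparison would rest on an unspecified subset of the 100 men

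*Protocol*

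**What the plan says.** **Outcome.** STI incidence is part of the aim in Part III, section 2 (Specific Aims and Study Objectives). Section 3 (Materials, Methods and Analysis) commits to a comparison: "we will also test whether GP4PrEP participants showed lower rates of STI incidence across the study period compared to AC".

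**Source.** Section 3 names one source: "STI incidence at each quarterly routine PrEP care visit will also be collected by extracting this data from participants' electronic medical records". Section 6 (Compensation / Reimbursement) treats HIV and STD testing as routine care, given by the participant's own doctor and billed to his insurer. The mailed blood-spot kits are analysed for TFV-DP and PEth only.

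**Recruitment.** Section 3 describes one route: "At the Miriam PrEP clinic, limited research staff who are co-located in the clinic" approach patients or hand out palm cards. Section 5 (Recruitment Methods) lists a variety of routes, "including social media advertisements, flyers and business cards, and from an existing database". Screening, consent and surveys are online.

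**Eligibility.** Section 4 (Participant Population) requires that a man be "currently prescribed and actively taking PrEP". None of the six inclusion or four exclusion criteria concerns where he receives care or whether his records can be released.

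**Access to records.** In Part VII, Appendix G (protected health information) is marked not applicable. In Part VIII, so are the HIPAA authorization and the data use agreement. In Part V, the questions on the source and type of secondary data are answered the same way.

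**The concern.** The way men enter the trial and the way this outcome is measured do not fit together. A man who answers an advertisement, takes PrEP from a provider unconnected with the study and meets every criterion can enrol and be randomised without the team ever having a stated means of seeing his STI results. No second source is described that would cover him.

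At stake is one of the outcomes in the aim. The other outcomes are collected by survey or post from everyone, so the drinking and adherence comparisons are designed to use all 100 men. The STI comparison would use however many records are retrieved, a number the protocol neither sets nor allows anyone to predict. A later analysis plan can say how to handle missing results, but it cannot supply results that were never collected.

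**Working it through.** **1. The passages side by side**

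| Element | What the protocol fixes | Where |
|---|---|---|
| Who can enter | Any man on prescribed PrEP who meets the criteria, wherever he is in care | Part III, sections 4 and 5 |
| How drinking and adherence are measured | Online surveys and mailed blood-spot kits, for everyone | Part III, section 3 |
| How STI is measured | Medical records of routine visits | Part III, section 3 |
| Permission to use records | Marked not applicable | Parts VII and VIII |

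The first row admits men from any provider, and the third needs each provider's record. The fourth offers no means of getting it. The not-applicable entries cover the whole study, so strictly the access route is undocumented for patients of the named clinic too. The gap is widest for men in care elsewhere, because the study has no stated link with their providers.

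**2. Size of the loss of precision**

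The protocol gives no power, STI rate or event count for this outcome, so there is no figure of its own to reproduce. It also gives no split by recruitment route. Let f be the share of men without a retrieved record, an assumption taken as equal in both arms. With 100 men randomised 1:1, the number analysed is 100 × (1 − f). The standard error of the between-arm comparison is multiplied by 1/√(1 − f).

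| f (assumed) | Men with STI data | Multiplier of standard error | Increase |
|---|---|---|---|
| 0 | 100 | 1/√1.00 = 1.00 | none |
| 25% | 75 | 1/√0.75 = 1.155 | about 15% |
| 50% | 50 | 1/√0.50 = 1.414 | about 41% |
| 75% | 25 | 1/√0.25 = 2.00 | 100% |

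**3. What that means for power (illustration only)**

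This is a comparison of two proportions, two-sided alpha 0.05, with 50 × (1 − f) men per arm. The STI risks are assumptions.

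| Assumed risks | f = 0 | f = 25% | f = 50% | f = 75% |
|---|---|---|---|---|
| 40% v 20% | 0.590 | 0.471 | 0.335 | 0.187 |
| 30% v 15% | 0.434 | 0.340 | 0.242 | 0.140 |
| 20% v 10% | 0.286 | 0.225 | 0.164 | 0.102 |

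Power is modest even with complete data, which is acceptable for an exploratory outcome. It does mean there is little precision to spare. The point itself does not depend on these figures.

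**The case against.** **A record should exist for every man.** All participants are on prescribed PrEP, and section 6 assumes quarterly visits with testing for all of them. Section 3 speaks of participants' records in general and does not confine extraction to the named clinic. A reader might infer that STI results cannot be obtained for men in care elsewhere. The documents do not support that, since a signed release could reach those records. What stands is narrower: the protocol states no route.

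**A route may sit in material not shown.** Consent pages were removed, and the survey measures are an attachment. A release or self-reported STI items could be there. That is possible, but the application itself marks the HIPAA authorization and Appendix G as not applicable, and section 3 names records as the source. The visible text points against a release.

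**The recruitment passages do not conflict.** A reader might infer that section 5 contradicts the clinic route in section 3. It does not. Its list is introduced as a non-exhaustive one, and it refers to palm cards, which section 3 has clinic staff handing out. The two sections can stand together.

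**Nothing says a missing record counts as no STI.** A reader might infer dilution from such scoring. The protocol contains no such rule. If it were applied with equal f in both arms, it would shrink a risk difference but leave a ratio unchanged, since (1 − f)p₁ / [(1 − f)p₂] = p₁/p₂. No bias of this kind is claimed here.

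**The consequence is limited.** The study is exploratory, STI is the last outcome listed, and randomisation should roughly balance record access between arms. All of this stands, and it limits the severity. It does not remove the gap.

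**Conclusion.** The point holds in this form: the STI comparison depends on medical records, entry does not depend on those records being obtainable, and the protocol states no means of obtaining them. As written, the comparison would rest on an unspecified part of the 100 men.

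The harm is lost precision and a restricted population for one exploratory outcome. The standard error rises by about 15%, 41% or 100% if 25%, 50% or 75% of men lack a retrieved record. Those shares are assumptions, as is their equality across arms. No systematic bias between arms is shown, and the drinking, PEth and TFV-DP outcomes are unaffected. The change should be made because it is cheap and has to be in place while data are being collected.

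**What to change.** 1. At baseline, before randomisation, record where each man receives PrEP care and obtain his authorization to access those records. Correct the entries for Appendix G, the HIPAA authorization and, where a provider requires one, the data use agreement.
2. Add STI test dates, results and diagnoses since the last survey to the existing 3- and 6-month online surveys for all men, as the source where a record is not retrieved. If the attached measures already contain such items, name them in section 3 as that source.
3. Report the record-based comparison as covering only men with retrieved records, with the number in each arm.

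**Cost.** A few survey items, a release form and corrected application entries. Recruitment and sample size are unchanged. Self-reported STI results are less reliable than records, and the record-based comparison will be stated openly as covering fewer than 100 men if some records are not retrieved.
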